C. trachomatis	Chlamydia trachomatis
CVD	Cardiovascular Disease
DAG	Directed Acyclic Graph
dbGaP	Database of Genotypes and Phenotypes
DHHS	Department of Health and Human Services
DMFS	Decayed, Missing, and Filled Surfaces
DMC	Data Management Center
DNA	Deoxyribonucleic Acid
DRC	Data Resources Core
DSM-IV	Diagnostic and Statistical Manual of Mental Disorders-IV
EBV	Epstein-Barr virus
EDTA	Ethylenediaminetetraacetic Acid
FDA	Food and Drug Administration
FGF	Fibroblast Growth Factor
GAD-7	Generalized Anxiety Disorder 7-Item Scale
GCP	Good Clinical Practice
GDS	Genomic Data Sharing
GED	General Educational Development
GEE	Generalized Estimating Equation
GINA	Genetic Information Nondiscrimination Act
GWAS	Genome-Wide Association Studies
GYN	Gynecological
HDL	High-Density Lipoprotein
HECC	Health Education and Community Core
HIPAA	Health Insurance Portability and Accountability Act
HIV	Human Immunodeficiency Virus

HLA	Human Leukocyte Antigen
HLC	Harvard Longwood Campus
HOMA-IR	Homeostatic Model Assessment of Insulin Resistance
HOPE	Health Outcomes around Pregnancy and Exposure to HIV/ARVs
HPV	Human Papillomavirus
HSIL	High-Grade Squamous Intraepithelial Lesions
HSPH	Harvard T. H. Chan School of Public Health
HSV	Herpes Simplex Virus
HTTPS	Hypertext Transfer Protocol Secure
IATA	International Air Transport Association
ICF	Informed Consent Form
ICH	International Council for Harmonisation of Technical Requirements for Pharmaceuticals for Human Use
IL-12	Interleukin-12
IMPAACT	International Maternal Pediatric Adolescent AIDS Clinical Trials Network
INSTI	Integrase Inhibitor
IRB	Institutional Review Board
LAR	Legally Authorized Representative
LDL	Low-Density Lipoprotein
LDMS	Laboratory Data Management System
LEGACY	Longitudinal Epidemiologic Study to Gain Insight into HIV/AIDS in Children and Youth
LOESS	Locally Estimated Scatterplot Smoothing
LPC	Laboratory Processing Chart
LSIL	Low-Grade Squamous Intraepithelial Lesions
MNPP	Manual of Network Policies and Procedures
MSM	Men who have Sex with Men
NaF/K oxalate	Sodium Fluoride/Potassium Oxalate
N. gonorrhoeae	Neisseria gonorrhoeae
NCI	The National Cancer Institute
NHLBI	The National Heart Lung and Blood Institute
NIAAA	The National Institute on Alcohol Abuse and Alcoholism
NIAID	The National Institute of Allergy and Infectious Diseases
NICHD	The Eunice Kennedy Shriver National Institute of Child Health and Human Development
NIDA	The National Institute on Drug Abuse
NIDCD	The National Institute of Deafness and Other Communication Disorders
NIDCR	The National Institute of Dental and Craniofacial Research
NIH	The National Institutes of Health
NIMH	The National Institute of Mental Health
NINDS	The National Institute of Neurological Disorders and Stroke
NNRTI	Non-Nucleoside Reverse Transcriptase Inhibitor
NRTI	Nucleoside Reverse Transcriptase Inhibitor
NtRTI	Nucleotide Reverse Transcriptase Inhibitor
OAR	The National Institutes of Health Office of AIDS Research
OD	The National Institutes of Health Office of the Director
OHD	Hydroxy-Vitamin D
OHRP	Office of Human Research Protection
OR	Odds Ratio
ORARC	Office of Regulatory Affairs and Research Compliance

OSHA	Occupational Safety and Health Administration
PACTG	Pediatric AIDS Clinical Trial Group
Pap	Papanicolaou Test
PBMCs	Peripheral Blood Mononuclear Cells
PDAY	Pathobiological Determinants of Atherosclerosis in Youth
PHACS	Pediatric HIV/AIDS Cohort Study
PHEU	Living with Perinatal HIV Exposure without Perinatally Acquired HIV
PHQ-9	Patient Health Questionnaire-9
PHI	Protected Health Information
PHIV	Perinatally Acquired HIV
PI	Protease Inhibitor
PID	Participant Identification Number
PIN	Personal Identification Number
PMOC	PHACS Management Oversight Committee
PTA	Pure Tone Average
PrEP	Pre-Exposure Prophylaxis
PRIME-MD	Primary Care Evaluation of Mental Disorders
PTSD	Post-Traumatic Stress Disorder
QNS	Query and Notification System
QoL	Quality of Life
REACH	Reaching for Excellence in Adolescent Care and Health
SARS-CoV-2	Severe Acute Respiratory Syndrome Coronavirus 2
SES	Study Enrollment System
SID	Study Identification Number
sIRB	Single Institutional Review Board
SMARTT	Surveillance Monitoring for ART Toxicities
SNR	Signal-to-Noise Ratio
SSL	Secure Sockets Layer
STI	Sexually Transmitted Infection
TasP	Treatment as Prevention
T. vaginalis	Trichomonas vaginalis
“U = U”	“Undetectable equals Untransmittable”
vs.	Versus
WIN	Words-in-Noise
WITS	Women and Infants Transmission Study
WLHIV	Women Living with HIV
WLPHEU	Women Living with Perinatal HIV Exposure without Perinatally Acquired HIV
WLPHIV	Women Living with Perinatally Acquired HIV
YAPHEU	Young Adults Living with Perinatal HIV Exposure without Perinatally Acquired HIV
YAPHIV	Young Adults with Perinatally Acquired HIV
YPHEU	Youth Living with Perinatal HIV Exposure without Perinatally Acquired HIV
YPHIV	Youth with Perinatally Acquired HIV

**LIST OF APPROVED STUDIES MEETING THE ELIGIBILITY REQUIREMENT FOR
ENROLLMENT INTO AMP UP (PH300) PRIOR TO JANUARY 30, 2017**

- PHACS AMP
- PACTG 219C (*Opened to AMP Up enrollment in September 2015*)
- IMPAACT 1074 (*Opened to AMP Up enrollment in September 2015*)
- PHACS SMARTT – Youth living with perinatal HIV exposure without perinatally acquired HIV (YPHEU) and mothers with perinatally acquired HIV (PHIV) (*Opened to AMP Up enrollment in August 2016*)

Additional studies as approved by the AMP Up Protocol Team

This list will be updated and maintained on the PHACS website at <https://phacsstudy.org>.

As of January 30, 2017, enrollment in the “AMP Up young adult PHIV (YAPHIV)” cohort was opened to all eligible individuals not previously or currently enrolled in one of the approved studies.

Under the protocol version 2.0, enrollment in the “AMP Up young adults living with perinatal HIV exposure without perinatally acquired HIV (YAPHEU)” cohort is open to all eligible individuals at all AMP Up sites; previous enrollment in PHACS SMARTT or AMP is encouraged but not required.

STUDY ABSTRACT

Design:	This is a prospective cohort study designed to define the impact of human immunodeficiency virus (HIV) infection and antiretroviral therapy (ART) on young adults with perinatally acquired HIV (YAPHIV) as they transition into adulthood. A group of young adults living with perinatal HIV exposure without perinatally acquired HIV (YAPHEU) from a similar sociodemographic background and age distribution will be enrolled for comparison.
Population:	YAPHIV and YAPHEU who are at or beyond their 18 th birthday will be recruited at participating PHACS sites.
Sample Size:	
YAPHIV Cohort: Approximately 650 participantsYAPHEU Cohort: Approximately 200 participants
Primary Objectives:	
To identify infectious and non-infectious complications of HIV disease and toxicities resulting from long-term ART, including disease progression, immune dysfunction, viral resistance, end-organ disease, and mortality.To define the impact of HIV infection and ART on the long-term clinical outcomes in YAPHIV, including:
Metabolic abnormalities and risk factors for cardiovascular disease (CVD), including derangements in glucose and lipid metabolism, blood pressure, and body composition.STIs (Chlamydia (C.) trachomatis, Neisseria (N.) gonorrhoeae, Trichomonas (T.) vaginalis, syphilis, human papillomaviruses (HPV), genital and anal warts, and herpes simplex virus (HSV)) among males and females, and cervical HPV-associated pre-cancers and cancers and other vaginal microbiota, and pelvic inflammatory disease among females.Reproductive health, fertility, and pregnancy outcomes including perinatal transmission of HIV.To define the impact of perinatal HIV infection, its concomitant risk factors, and ART on long-term neurocognitive and behavioral health outcomes, including:
Mental health (both psychiatric disorders and emotional/behavioral functioning) and neurocognitive functioning.Health care behaviors, including adherence to ART, participation in health care services, and transition to adult clinical care.Risk behaviors, including sexual behavior and substance use (alcohol, tobacco, vaping, and licit and illicit drugs).Hearing and language impairments.Independent living skills, vocational and education achievement, life satisfaction, resilience, and health-related quality of life (QoL)
Domain-Specific Aims:	Infectious and Non-Infectious Complications of HIV and Its Treatment

- To evaluate the long-term immunologic and virologic course of YAPHIV, including immune competence and activation, disease progression, viral resistance, and the response to changes in therapy.
- To identify cofactors which impact the short- and long-term course of HIV disease, including incident co-infections and host genetics.
- To evaluate the incidence and course of HIV end-organ disease (i.e., renal, hepatic, cardiac, pulmonary, and peripheral and central nervous system) and HIV-associated malignancies and mortality of YAPHIV, and to describe the relationship of these outcomes with HIV virologic status, ART, immune impairment, and chronic immune activation.
- To contribute to HIV remission/cure studies by understanding the viral dynamics and compartmentalization of perinatally acquired HIV (PHIV) in the context of novel HIV therapeutics, age at ART initiation, long-term viral suppression, immunologic control, and the presence and size of the viral reservoir.
- To evaluate access to testing for severe acute respiratory syndrome coronavirus 2 (SARS-CoV-2), access to and acceptance of testing, treatment, and prevention strategies for other important infections among YAPHIV and YAPHEU.
- To assess vaccine acceptance among YAPHIV and YAPHEU, including receipt and intent to receive a SARS-CoV-2 vaccine and explore reasons for acceptance or hesitancy
- To define the oral health of YAPHIV and YAPHEU and to identify risk factors associated with declining oral health.
- Among YAPHIV, to determine risk behaviors for HIV transmission and their understanding of Undetectable equals Untransmittable (U = U) as an approach to the prevention of HIV transmission.
- Among YAPHEU, to determine their level of knowledge about and use of pre-exposure prophylaxis (PrEP) and their rates of HIV acquisition.

Metabolic Complications

- To evaluate longitudinal changes in parameters of cardiometabolic risk by HIV status (YAPHIV versus [vs.] YAPHEU), including body weight and composition, lipid levels, insulin sensitivity, blood pressure, and modified pathobiological determinants of atherosclerosis in youth (PDAY) scores (a predictor of atherosclerosis).
- Among YAPHIV, to evaluate the association of ART switches with changes in body weight and composition, lipid levels, insulin sensitivity, and blood pressure.
- To evaluate food insecurity and diet in YAPHIV and YAPHEU and their associations with body composition and metabolic outcomes. Among YAPHIV, to evaluate the associations of food security with adherence to ART and whether the association is mediated through engagement in clinical care.

Cardiopulmonary Complications

- To evaluate the distribution of PDAY scores for YAPHIV and YAPHEU and compare the distributions by HIV status, and to assess the association of PDAY scores and cardiac biomarkers with neurocognitive function as reflected by NIH Toolbox measures.
- To determine the association between pulmonary function and left and right ventricular structure and function.
- To determine the prevalence of marijuana and nicotine vaping in YAPHIV and YAPHEU and evaluate associations of vaping with presence of asthma, pulmonary disease, and hospitalization by PHIV status.

Sexually Transmitted Infections

- To evaluate access to testing and treatment for genital STIs and bacterial vaginosis, and the incidence of and risk factors for acquiring STIs (e.g., *C. trachomatis*, *N. gonorrhoeae*, *T. vaginalis*, syphilis, HPV, HSV) and microbiome dysbiosis including clinical bacterial vaginosis among YAPHIV and YAPHEU, and acquisition of HIV among YAPHEU.
- To evaluate the incidence of and risk factors for pelvic inflammatory disease among females.
- To evaluate the occurrence of high-grade squamous intraepithelial lesions (HSIL), external genital warts, and persistent cervical, oral, and anal high-risk HPV, and the factors associated with persistent anogenital or oral high-risk HPV, including the vaginal microbiome.

Reproductive Health

Among women living with PHIV (WLPHIV) and women living with PHEU (WLPHEU):

- To describe the use of pregnancy prevention methods and their associations with pregnancy and STI outcomes.
- To determine incidence of and factors associated with pregnancy intention.
- To examine pregnancy outcomes and factors associated with these outcomes.
- To identify rates of menstrual irregularities and risk factors for menstrual irregularity, including stress, hormonal disturbances, HIV-related health, and ART use.
- To determine the incidence of perinatal transmission of HIV.

Among WLPHIV, in comparison to women living with non-perinatally acquired HIV from the Health Outcomes around Pregnancy and Exposure to HIV/ARVs (HOPE) study:

- To evaluate individual, mental health, and interpersonal factors associated with unintended pregnancy, contraceptive discontinuation or non-use, discordant family planning behaviors and desires, and incident STIs.

- To compare factors associated with unintended pregnancy, contraceptive discontinuation or non-use, discordant family planning behaviors and desires, and incident STIs by mode of HIV acquisition (PHIV vs. non-PHIV).

Neurocognitive Functioning and Mental Health

- Among YAPHIV and YAPHEU, to describe the trajectories of cognitive functioning and mental health in young adulthood and examine factors associated with these trajectories.
- To identify the trajectories of co-occurring risks in cognitive, mental health, and behavioral health (sexual behaviors and drug and alcohol use) in young adulthood.
- To identify factors associated with trajectories of co-occurring risks in cognitive, mental, and behavioral health in young adulthood, including PHIV status, and individual, interpersonal and systemic influences experienced during childhood and adolescence including adverse childhood experiences (e.g., exposure to violence, neglect, etc.), and young adulthood experiences (e.g., racism, low levels of social support, etc.)
- To define the impact of the SARS-CoV-2 pandemic and its associated mitigation strategies on the mental health of participants affected by HIV.

Health Care Behaviors and Transition to Adult Health Care

- To describe factors associated with adherence to ART and health care and changes in adherence over time.
- Among YAPHIV, to estimate the associations between cognitive, mental health, and behavioral health (sexual, drug, and alcohol) risk trajectories during adolescence and ART adherence and viral suppression in young adulthood.
- To describe the transition from pediatric or adolescent to adult clinical care and to identify the individual, social, and health care system barriers and facilitators of adherence, access to and retention in adult health care, and clinical outcomes after transition (including sustained viral suppression).

Risk and Protective Behaviors

[figure not shown]
- To examine the prevalence, changes over time, and factors associated with sexual behaviors (including vaginal, oral, and anal intercourse, condom use, and multiple sexual partners), disclosure of HIV status, and knowledge of partner's HIV status.
- To examine the prevalence, changes over time, consequences of, and factors associated with use of licit (alcohol, tobacco) and illicit substances.
- To compare the prevalence and factors associated with sexual and substance use behaviors between YAPHIV and YAPHEU.

Transition to Adult Functioning and QoL

	
• To examine whether successful transition to adult functioning varies by HIV infection status.• To examine life satisfaction, resilience, health-related QoL, sleep, friendship, and successful adult functioning (including educational attainment, employment, and independent living) of YAPHIV and YAPHEU, and to identify childhood, adolescent and young adult factors associated with these outcomes.• To determine the association between trajectories of co-occurring mental health and behavioral risks with attainment of adult milestones, including employment and ongoing education.
Evaluations:	
Hearing and Language
 
• To assess changes in language acquisition from childhood to young adulthood in YAPHIV and YAPHEU and, among YAPHIV, the association of these changes with HIV disease severity and antiretroviral (ARV) exposure.• To determine how language abilities and hearing in adolescence predict employment status, educational status, reading abilities and life satisfaction in young adulthood.• To evaluate hearing sensitivity of YAPHIV and YAPHEU, and to evaluate the associations of ARV exposure and HIV disease severity with these outcomes. 
These visits are intended to be conducted in-person. If circumstances preclude an in-person visit, the visit can be conducted remotely, e.g., clinical assessment data will be collected through chart abstraction (when available), surveys and questionnaires may be completed via telephone (with Protocol Team approval), and research Aptima sexually transmitted infection (STI) test specimens may be self-collected and shipped to the clinical site.
 
• Annual chart abstraction will include interval medical diagnoses, ART history (participants with HIV only) and other medications, immunizations, social history, reproductive history, height, weight, blood pressure, and results of laboratory testing conducted for clinical care.• Annual web-based survey will collect information on socio-demographics, general health and health care-related, mental health, social determinants of health, reproductive health, sexual behaviors, substance use, and ARV medication adherence (participants with HIV only).

	
• Testing for STIs will be done annually in real-time at a local testing laboratory if results are not available from current chart abstraction. In addition, urine from males and vaginal swab (preferred) or urine from females will be collected annually for research Aptima STI testing. HIV testing will be offered to YAPHEU at the Years 3 and 9 in-person study visits.
Monitoring:	Routine team monitoring of any adverse impact of the study will rely on the PHACS Protocol Query and Notification System (QNS), a real-time, web-based interactive reporting system. Sites will also record and enter in the study database, all untoward effects associated with study participation, which will be reviewed by the Protocol Team.

STUDY SCHEMA

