2.2.5 Reproductive Health

Specific Aims:

Among WLPHIV and WLPHEU:

- To describe the use of pregnancy prevention methods and their association with pregnancy and STI outcomes.
- To determine incidence of and factors associated with pregnancy intention.
- To examine pregnancy outcomes and factors associated with these outcomes.
- To identify rates of menstrual irregularities and risk factors for menstrual irregularity, including stress, hormonal disturbances, HIV-related health, and ART use.
- To determine the incidence of perinatal transmission of HIV.

Among WLPHIV, in comparison to women living with non-perinatally acquired HIV from the Health Outcomes around Pregnancy and Exposure to HIV/ARVs (HOPE) study:

- To evaluate individual, mental health, and interpersonal factors associated with unintended pregnancy, contraceptive discontinuation or non-use, discordant family planning behaviors and desires, and incident STIs.
- To compare factors associated with unintended pregnancy, contraceptive discontinuation or non-use, discordant family planning behaviors and desires, and incident STIs by mode of HIV acquisition (PHIV vs. non-PHIV).

Hypotheses:

- The majority of WLPHIV who use pregnancy prevention will choose long-acting contraceptives. These methods will be superior to combined oral contraceptive pill in preventing pregnancies; however, they will be linked to lack of condom use and higher STI rates.
- Predictors of pregnancy intention will be similar for WLPHIV and WLPHEU and will include older age and perceived close relationship to partner.
- Young WLPHIV who are not on contraceptives will be more likely than young WLPHEU to have anovulatory cycles (defined as having cycles < 21 and > 35 days). Irregular cycles will be affected by stress, depression, BMI, and substance use, and for WLPHIV, CD4 cell count and ART adherence.
- Young WLPHIV will have fewer pregnancies than WLPHEU after adjusting for BMI, STI history, and substance use. Vaginal dysbiosis will be associated with fewer pregnancies.
- Young pregnant WLPHIV will have higher spontaneous abortion rates than WLPHEU after adjusting for substance use. Vaginal dysbiosis will play a role in this increased rate of spontaneous abortion.
- The rate of perinatal transmission of HIV will be low.

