4.1 YAPHIV Cohort

4.1.1 Inclusion Criteria

To be considered eligible for enrollment, an individual must meet all the criteria listed below:

- Has perinatal HIV infection as documented in the medical record.
- Is at or beyond their 18th birthday at the time of informed consent.
- Is willing to provide access to existing medical records.
- At least one of the following is true:
 - Previously enrolled in any of the studies included on the list of approved studies (see list of approved studies meeting the eligibility requirement for enrollment into AMP Up on page 15), or
 - Available medical record documentation* since early childhood, if possible, but no later than 12 years of age. Medical records must also be available starting no later than 2 years after HIV diagnosis and include:
 - ART exposure history,
 - Opportunistic infection prophylaxis exposure history,
 - Viral load and CD4 cell count history, and
 - Major medical events history.

*Medical record documentation should consist of all existing records from when the participant entered care with no gaps in existing records of more than 12 months.

- Is willing to participate and provide legal written consent.

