4.4 Participant Recruitment

Potential participants will be identified by the study personnel at the participating sites. Clinical staff members such as case managers and healthcare providers at clinical sites will be made aware of the eligibility criteria of the study. Potential participants will be identified and referred to the clinical research team for potential enrollment. A research staff member will approach potential participants to provide an overview of the study, gauge the potential participant's interest in participating, and determine their eligibility. Clinical research teams will be encouraged to approach all eligible former AMP and SMARTT participants and other eligible YAPHIV and YAPHEU regarding participation in this study. The major criterion for approval is the completeness of documentation of ART exposure history, viral load and CD4 cell count, and major medical events.

Young adults formerly enrolled in pediatric protocols will be approached for willingness to enroll in adult protocols once they reach the age of majority. This is a common practice at our clinical sites.

A common reason reported on pediatric studies for discontinuation is that the caregiver is unable to commit the time required for study visits. These families typically continue to receive clinical care at the clinical site and maintain relationships with study staff. Participants often welcome the opportunity to enroll in research studies once they have reached the age of majority and can consent on their own behalf.

Enrollment will remain open until the required number of participants is enrolled or until enrollment is closed by the Protocol Team in order to allow adequate duration of follow-up of participants.

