12.2.5 Reproductive Health

The analysis of reproductive health outcomes will focus on estimating the prevalence and incidence of pregnancies (intended and unintended); pregnancy outcomes (live birth, induced abortion, spontaneous abortion, fetal death); the prevalence and incidence of menstrual irregularities; and the incidence of perinatal HIV transmission.

We will calculate prevalence estimates based on those with the specific outcome of interest divided by those with measurements for that outcome, along with 95% CIs. Incidence estimates will be calculated under a Poisson distribution based on participant-years of follow-up.

The prevalence of each outcome will be compared between the YAPHIV and the YAPHEU comparison group using chi-square tests as crude analyses and using logistic regression models for each separate outcome as a function of HIV status controlling for important demographic, and clinical and social factors (including but not limited to socioeconomic factors, partner characteristics, viral load, adherence, depression, and other behaviors).

Factors associated with prevalence of each outcome will be identified using logistic regression models. Factors associated with the incidence of each outcome will be identified using Cox-proportional hazards models. Factors associated with changes in reproductive health measures over time will be identified using GEE models, or mixed effect models when possible, to account for correlation between assessments on the same participant.

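### Women with PHIV can enter the YAPHIV cohort as former SMARTT mothers, and Section 12.2.5 then compares pregnancy between the cohorts without setting aside pregnancies before Entry

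*Protocol*

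**What the plan says.** **Entry.** The list of approved studies at the front of the protocol names, under SMARTT, "Youth living with perinatal HIV exposure without perinatally acquired HIV (YPHEU) and mothers with perinatally acquired HIV (PHIV"). The two cohorts thus draw on SMARTT differently: PHEU as exposed offspring, women with PHIV as mothers. Section 4.1.1 asks YAPHIV to meet at least one of two conditions. One is "Previously enrolled in any of the studies included on the list of approved studies". The other is a medical record reaching back to age 12 or earlier, starting within 2 years of HIV diagnosis, with no gap over 12 months. Section 4.0 adds Protocol Team approval for anyone not previously in a listed study. Section 4.2.1 (YAPHEU) has no condition linked to childbirth.

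**Later opening.** From 30 January 2017 YAPHIV enrolment "was opened to all eligible individuals not previously or currently enrolled in one of the approved studies". For YAPHEU, under version 2.0, "previous enrollment in PHACS SMARTT or AMP is encouraged but not required".

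**Hypotheses and analysis.** Section 2.2.5 expects that "Young WLPHIV will have fewer pregnancies than WLPHEU after adjusting for BMI, STI history, and substance use" and that "Young pregnant WLPHIV will have higher spontaneous abortion rates than WLPHEU after adjusting for substance use". Section 12.2.5 covers prevalence and incidence of pregnancy, and pregnancy outcomes. On the between-cohort test it says: "The prevalence of each outcome will be compared between the YAPHIV and the YAPHEU comparison group using chi-square tests as crude analyses", followed by logistic regression on HIV status. The list of adjustment factors is open-ended. Parity at Entry and entry route are not named, and no window for counting pregnancies is set.

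**The concern.** Part of one cohort may be selected on the outcome being compared. A woman with PHIV who has an incomplete childhood record and no other listed study can enter if she was a SMARTT mother, but not otherwise. Nothing comparable operates among YAPHEU. If the birth that brought her into SMARTT is then counted as a pregnancy and a live birth, the YAPHIV side is raised on both.

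Both effects run against the stated hypotheses. Fewer pregnancies in WLPHIV would be harder to see, and a higher spontaneous abortion rate would be diluted by live births that were certain to be present. Adding covariates to the regression does not by itself repair a prevalence contrast when entry depended on the outcome.

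**Working it through.** The plan gives no figure for this point, so there is none to reproduce. What can be shown is a range.

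**Inputs.**
- The share f of YAPHIV women who entered only as SMARTT mothers is not stated; 5%, 10% and 20% are assumed.
- Ever-pregnant prevalence p is assumed to be 30% in both cohorts, so the true odds ratio is 1.00.
- k is the fraction of those mothers who are surplus, that is, over and above the mothers that unselected recruitment would have brought in. It is unknown, between 0 and 1.

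**Formula.** Observed YAPHIV prevalence = kf + (1 − kf)p. The odds ratio compares this with p; the comparison odds are 0.30/0.70 = 0.4286.

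**Lower limit, k = 0.** SMARTT mothers are simply part of the 30%. Observed 30% vs 30%, OR 1.00 at any f.

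**Upper limit, k = 1.**
- f = 5%: 0.05 + 0.95 × 0.30 = 33.5%; OR 1.18
- f = 10%: 0.10 + 0.90 × 0.30 = 37.0%; OR (0.37/0.63)/0.4286 = 1.37
- f = 20%: 0.20 + 0.80 × 0.30 = 44.0%; OR 1.83

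At f = 10% the range is therefore 1.00 to 1.37. If half of those mothers are surplus, kf = 5% and the OR is 1.18. The base rate matters too: at f = 10% the upper limit is 1.56 for p = 20% and 1.28 for p = 40%.

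**When the hypothesis is true.** Let the true OR be 0.70, so YAPHIV odds are 0.70 × 0.4286 = 0.30 and prevalence is 0.30/1.30 = 23.1%. With f = 10% and k = 1, observed is 0.10 + 0.90 × 0.231 = 30.8%, OR 1.04. With k = 0 it stays 0.70.

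**Pregnancy outcomes, upper limit only.** Take a 24% spontaneous abortion share (the figure Section 1.1.6 cites for women living with HIV), and assume 0.5 other pregnancies per woman plus one certain live birth per SMARTT mother. At f = 10%, pregnancies per woman are 0.10 × 1.5 + 0.90 × 0.5 = 0.60 and spontaneous abortions 0.24 × 0.5 = 0.12, so the share appears as 0.12/0.60 = 20.0%. At f = 20% it is 0.12/0.70 = 17.1%. With k = 0 it remains 24%.

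**Testing the obvious remedy.** Suppose all SMARTT mothers are dropped from YAPHIV while every YAPHEU mother is kept. If mothers were not over-recruited, a 10% share leaves (0.30 − 0.10)/0.90 = 22.2% vs 30%, OR 0.67. A 20% share leaves 0.10/0.80 = 12.5%, OR 0.33. Blanket exclusion can create the hypothesised deficit.

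**The case against.** **Motherhood is not a gate for the cohort.** SMARTT was opened to AMP Up in August 2016 and YAPHIV enrolment was opened generally on 30 January 2017, about five months later. Since then a SMARTT mother may also qualify through her records, and some will have been in AMP, PACTG 219C or IMPAACT 1074. This stands and dilutes the effect. It does not remove it, because Section 4.1.1 still spares SMARTT mothers the record requirement.

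**Section 4.4 is even-handed.** It says "Clinical research teams will be encouraged to approach all eligible former AMP and SMARTT participants", and the same sentence goes on to include other eligible YAPHIV and YAPHEU. A reader might infer that sites are directed to seek out mothers; the text does not support that. PHEU mothers may also enrol, although motherhood is not what qualifies them.

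**Incidence is largely protected.** Section 12.2.5 bases it on participant-years of follow-up, which does not count the qualifying birth. This stands. What remains is indirect, through parity, proven fertility and contraceptive intentions.

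**This belongs in the statistical analysis plan.** That plan is not at hand; it could define the pregnancy window, and the open covariate list allows parity. Section 12.2.5 also does not say that prevalence means ever pregnant. These points lower the priority. But the protocol itself creates the asymmetric entry and commits to the between-cohort prevalence test, so more than a detail is at issue.

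**Conclusion.** The concern holds in a limited form. Entry to YAPHIV can depend on having given birth, entry to YAPHEU cannot, and the planned prevalence and pregnancy-outcome contrasts do not set aside pregnancies before Entry. Any resulting bias is towards more pregnancies and more live births in YAPHIV.

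Its size cannot be fixed from the protocol. Under the 30% and 10% assumptions it lies between none and an OR of 1.37. The distortion is direct only for measures that include pregnancies before Entry.

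Three stronger readings are tempting and not supported:
- That a real deficit in WLPHIV will be hidden or reversed. This needs every SMARTT mother to be surplus, and neither their number nor their over-recruitment is documented.
- That contraception, condom use, education or employment comparisons are biased too. This is plausible, but nothing in the protocol shows it.
- That all SMARTT mothers should be excluded from the lifetime comparison. That selects on the outcome in one cohort only.

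**What to change.** In Section 12.2.5:
1. Base YAPHIV vs YAPHEU comparisons of pregnancy and pregnancy outcomes on pregnancies conceived after AMP Up Entry, and take account of parity at Entry.
2. Record whether each YAPHIV woman was enrolled in SMARTT as a mother before Entry, and whether she met any other eligibility route. The date matters, because Section 4.7 encourages enrolment of participants' children in SMARTT along with their mothers.
3. Run a sensitivity analysis omitting only YAPHIV women who met no other route.
4. Report lifetime prevalence descriptively by cohort, and do not drop all SMARTT mothers from it.

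The cost is fewer pregnancies in the between-cohort contrast, hence less precision, and a little more analysis work. Section 4.6 keeps the PHACS identifier for earlier participants, so prior SMARTT enrolment should be traceable. Who may enrol and the analyses within YAPHIV do not change.
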